7.4 JUSTIFICATION FOR SENSITIVE PROCEDURES

Titration schedule of the drug is designed to minimize adverse events as well as withdrawal symptoms.

7.5 CONCOMITANT MEDICATIONS, TREATMENTS, AND PROCEDURES

7.5.1 PRECAUTIONARY MEDICATIONS, TREATMENTS, AND PROCEDURES Use of pain medicines like NSAIDs, and Aspirin. Use of blood thinner including Aspirin and warfarin.

7.6 PROHIBITED MEDICATIONS, TREATMENTS, AND PROCEDURES

Subjects will be asked to avoid starting any new medications that may be associated with interaction or lead to serotonin syndrome. These include antidepressants, antipsychotics, other SSRI agents, migraine medicine- particularly "Triptan family", linezolid, methylene blue. These medication can lead to "serotonin syndrome".

b: Subjects enrolled from neurology clinic

Version 01.2 Protocol:201607761 06/28/2017

7.7 PROPHYLACTIC MEDICATIONS, TREATMENTS, AND PROCEDURES

NA

7.8 RESCUE MEDICATIONS, TREATMENTS, AND PROCEDURES

NA

7.9 PARTICIPANT ACCESS TO STUDY AGENT AT STUDY CLOSURE

NA

8 ASSESSMENT OF SAFETY

8.1 SPECIFICATION OF SAFETY PARAMETERS

All serious and non serious adverse events will be recorded

8.1.1 DEFINITION OF ADVERSE EVENTS (AE)

Adverse event means any untoward medical occurrence associated with the use of an intervention, whether or not considered intervention-related.

8.1.2 DEFINITION OF SERIOUS ADVERSE EVENTS (SAE)

An AE or suspected adverse reaction is considered "serious" if, in the view of the investigator, it results in any of the following outcomes: death, a life-threatening adverse event, inpatient hospitalization or prolongation of existing hospitalization, a persistent or significant physical or mental incapacity including worsening depression, increase suicidal thoughts or actions, acting aggressive or violent, or a congenital anomaly/birth defect. Important medical events that may not result in death, be life-threatening, or require hospitalization may be considered serious when, based upon appropriate medical judgment, they may jeopardize the patient or subject and may require medical or surgical intervention to prevent one of the outcomes listed in this definition. Examples of such medical events include allergic reactions including angioedema of face, tongue, mouth, and bronchospasm requiring intensive treatment in an emergency room or at home, or increased seizure frequency from baseline that do not result in inpatient hospitalization.

8.1.3 DEFINITION OF UNANTICIPATED PROBLEMS (UP)

Unanticipated problems (UP) per OHRP, are any incident, experience, or outcome that meets all of the following criteria:

- Unexpected in terms of nature, severity, or frequency given (a) the research procedures that are described in the IRB-approved research protocol and informed consent document; and (b) the characteristics of the participant population being studied;
- Related or possibly related to participation in the research ("possibly related" means there is a reasonable possibility that the incident, experience, or outcome may have been caused by the procedures involved in the research); and

Version 01.2 Protocol:201607761 Version 20.2 Version 01.2

• Suggests that the research places participants or others at a greater risk of harm (including physical, psychological, economic, or social harm) than was previously known or recognized. This study will use the OHRP definition of UP

8.2 CLASSIFICATION OF AN ADVERSE EVENT

8.2.1 SEVERITY OF EVENT

For AEs not included in the protocol defined grading system, the following guidelines will be used to describe severity.

- **Mild** Events require minimal or no treatment and do not interfere with the participant's daily activities.
- **Moderate** Events result in a low level of inconvenience or concern with the therapeutic measures. Moderate events may cause some interference with functioning.
- **Severe** Events interrupt a participant's usual daily activity and may require systemic drug therapy or other treatment. Severe events are usually potentially life-threatening or incapacitating.

8.2.2 RELATIONSHIP TO STUDY AGENT

For all collected AEs, the clinician who examines and evaluates the participant will determine the AE's causality based on temporal relationship and his/her clinical judgment. The degree of certainty about causality will be graded using the categories below.

- **Definitely Related** There is clear evidence to suggest a causal relationship, and other possible contributing factors can be ruled out. The clinical event, including an abnormal laboratory test result, occurs in a plausible time relationship to drug administration and cannot be explained by concurrent disease or other drugs or chemicals. The response to withdrawal of the drug (dechallenge) should be clinically plausible. The event must be pharmacologically or phenomenologically definitive, with use of a satisfactory rechallenge procedure if necessary.
- **Probably Related** There is evidence to suggest a causal relationship, and the influence of other factors is unlikely. The clinical event, including an abnormal laboratory test result, occurs within a reasonable time after administration of the drug, is unlikely to be attributed to concurrent disease or other drugs or chemicals, and follows a clinically reasonable response on withdrawal (dechallenge). Rechallenge information is not required to fulfill this definition.
- **Possibly Related** There is some evidence to suggest a causal relationship (e.g., the event occurred within a reasonable time after administration of the trial medication). However, other factors may have contributed to the event (e.g., the participant's clinical condition, other concomitant events). Although an AE may rate only as "possibly related" soon after discovery, it can be flagged as requiring more information and later be upgraded to "probably related" or "definitely related," as appropriate.
- Unlikely to be related A clinical event, including an abnormal laboratory test result, whose temporal relationship to drug administration makes a causal relationship improbable (e.g., theevent did not occur within a reasonable time after administration of the trial medication) and inwhich other drugs or chemicals or underlying disease provides plausible explanations (e.g., the participant's clinical condition, other concomitant treatments).

Version 01.2 Protocol:201607761 06/28/2017

• **Not Related** – The AE is completely independent of study drug administration, and/or evidenceexists that the event is definitely related to another etiology. There must be an alternative, definitive etiology documented by the clinician.

8.2.3 EXPECTEDNESS

PI, will be responsible for determining whether an AE is expected or unexpected. An AE will be considered unexpected if the nature, severity, or frequency of the event is not consistent with the risk information previously described for the study agent.

8.3 TIME PERIOD AND FREQUENCY FOR EVENT ASSESSMENT AND FOLLOW-UP

The occurrence of an AE or SAE may come to the attention of study personnel during study visits and interviews of a study participant presenting for medical care, or upon review by a study monitor. All AEs including local and systemic reactions not meeting the criteria for SAEs will be captured on the appropriate RF. Information to be collected includes event description, time of onset, clinician's assessment of severity, relationship to study product (assessed only by those with the training and authority to make a diagnosis), and time of resolution/stabilization of the event. All AEs occurring while on study must be documented appropriately regardless of relationship. All AEs will be followed to adequate resolution.

Any medical condition that is present at the time that the participant is screened will be considered as baseline and not reported as an AE. However, if the study participant's condition deteriorates at any time during the study, it will be recorded as an AE. UPs will be recorded in the data collection system throughout the study.

Changes in the severity of an AE will be documented to allow an assessment of the duration of the event at each level of severity to be performed. AEs characterized as intermittent require documentation of onset and duration of each episode.

The PI will record all reportable events with start dates occurring any time after informed consent is obtained until 7 days after the last day of study participation. At each study visit/followup phone visit, the investigator will inquire about the occurrence of AE/SAEs since the last visit. Events will be followed for outcome information until resolution or stabilization.

8.4 REPORTING PROCEDURES

8.4.1 ADVERSE EVENT REPORTING

Adverse events that are serious will reported to independent medical examiner and IRB.

8.4.2 SERIOUS ADVERSE EVENT REPORTING

The study clinician will complete a SAE Form within the following timelines:

Version 01.2 Protocol:201607761 Version 201.2

• All deaths and immediately life-threatening events, whether related or unrelated, will be recorded on the SAE Form and submitted to the independent medical examiner within 24 hours of site awareness. See **Section 1**, **Key Roles** for contact information.

• Other SAEs regardless of relationship, will be submitted to independent medical examiner within 72 hours of site awareness.

All SAEs will be followed until satisfactory resolution or until the site investigator deems the event to be chronic or the adherence to be stable. Other supporting documentation of the event may be requested by the independent medical examiner and should be provided as soon as possible. The principal investigator will be responsible for notifying IRB of any unexpected fatal or life-threatening suspected adverse reaction as soon as possible but in no case later than 7 calendar days after site awareness.

8.4.3 UNANTICIPATED PROBLEM REPORTING

Incidents or events that meet the OHRP criteria for UPs require the creation and completion of an UP report form. The investigator shall report UPs to the IRB and to the IME. The UP report will include the following information:

- Protocol identifying information: protocol title and number, PI's name, and the IRB projectnumber;
- A detailed description of the event, incident, experience, or outcome;
- An explanation of the basis for determining that the event, incident, experience, or outcomerepresents an UP;
- A description of any changes to the protocol or other corrective actions that have been taken orare proposed in response to the UP.

To satisfy the requirement for prompt reporting, UPs will be reported using the following timeline:

- UPs that are lifethreatening or death, will be reported to the IRB and to the IME within 1 day of the investigator becoming aware of the event. But other SAEs, will be reported within 3 days of the investigator becoming aware of the event.
- Any other UP will be reported to the IME only within 7 days of the investigator becoming aware of the problem.

8.4.4 REPORTING OF PREGNANCY

Women with potential for being pregnant will be screened to rule out active pregnancy using standard questionnaire and urinary pregnancy test. If pregnancy is reported by the participant while on study medicine, the medicine will be discontinued and she shall be referred for high risk obstetric clinic.

Each pregnancy must be reported by the Investigator to the IME on the initial pregnancy report form within 30 days after becoming aware of the pregnancy. The Investigator must follow-up and document the course and the outcome of all pregnancies even if the subject was withdrawn from the clinical study or if the clinical study has finished.

Version 01.2 Protocol:201607761 06/28/2017

All outcomes of pregnancy must be reported by the Investigator to the Sponsor on the pregnancy outcome report form within 30 days after he/she has gained knowledge of the normal delivery or elective abortion.

8.5 STUDY HALTING RULES

Administration of study agent will be halted when three grade 3 (severe) AEs determined to be "probably related" are reported to the IME. The IME will notify the study sponsor and investigators immediately when the third grade 3 event is reported and enrollment screens will stop accepting new study participants. The study sponsor will provide the IME with AE listing reports within 24 hours. The IME will provide recommendations for proceeding with the study to the study sponsor. The study sponsor may inform the FDA of the temporary halt and the disposition of the study.

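### Read literally, the halting rule in 8.5 leaves out severe AEs rated definitely related, and it counts events that not every related severe AE is sure to reach in time: a minor correction to the protocol's only numerical safety rule

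*Combined protocol and SAP*

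**What the plan says.** Section 8.5 halts administration of study agent when "three grade 3 (severe) AEs determined to be 'probably related' are reported to the IME". Its second sentence has the IME notify the sponsor and investigators "when the third grade 3 event is reported and enrollment screens will stop accepting new study participants". The sponsor then supplies AE listings to the IME within 24 hours, and the IME recommends how to proceed.

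Section 8.2.2 grades causality in five categories. The top one, definitely related, is defined separately from probably related: "There is clear evidence to suggest a causal relationship, and other possible contributing factors can be ruled out". The section treats the categories as an ordered scale, since a possibly related event can "later be upgraded to 'probably related' or 'definitely related,' as appropriate".

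On reporting, 8.4.1 says "Adverse events that are serious will reported to independent medical examiner and IRB". Section 8.4.2 sets 24 hours for deaths and immediately life-threatening events, and for the rest says "Other SAEs regardless of relationship, will be submitted to independent medical examiner within 72 hours of site awareness". Section 8.4.3 sends unanticipated problems to the IME within 1, 3 or 7 days, and 8.4.4 covers pregnancies. For non-serious events, 8.3 says only "All AEs including local and systemic reactions not meeting the criteria for SAEs will be captured on the appropriate RF".

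**The concern.** A halting rule is applied as written, often by someone who did not draft it. Two features of this one could delay a halt.

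First, the causality term in 8.5 matches one named category in 8.2.2, with no 'at least' or 'or higher'. Taken literally, the events with the strongest causal evidence do not count.

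Second, the count is of events that have reached the IME, yet the timed reports are defined by seriousness or unexpectedness, while the rule is defined by severity and relatedness. These are different attributes, so an event can qualify for the count without qualifying for a report.

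This is the only numerical halting rule. Section 9 (clinical monitoring) is marked not applicable, 10.4.7 plans no interim analysis, and 10.4.7.1 gives no statistical plan for safety review. What is at stake is continued dosing, and possibly continued enrolment, after three related severe AEs have occurred.

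**Working it through.** The protocol gives no operating characteristic for the rule, so there is no figure to reproduce. The check is mainly textual.

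**1. Causality term.** Section 8.5 names one grade and 8.2.2 places another above it. Nothing in 8.5 extends the count upward, so the literal trigger omits definitely related events.

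**2. Second sentence of 8.5.** It mentions the third event without a causality term. Two readings are open:
- It refers back to the first sentence. The enrolment stop and IME notification then share the omission.
- It stands alone. The third severe AE of any causality then brings IME notification, the enrolment stop, the 24-hour listing and an IME recommendation. Definitely related events already reported would be before the IME, which softens the gap for dosing.

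The text does not settle which is meant.

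**3. Route to the IME.** Consider severe insomnia or severe diarrhoea, both listed as effects of fluoxetine in 2.3.1, judged related, expected and not serious.
- *SAE route (8.4.1, 8.4.2):* does not apply, because the event is not serious.
- *Unanticipated problem route (8.1.3, 8.4.3):* does not apply, because all criteria must be met, including unexpectedness.
- *Form under 8.3:* records the event, with no onward report.
- *Unblinding report (10.6.3):* reports the unblinding, with no deadline and no causality rating.
- *IME assessment of safety data (8.6):* no schedule.
- *Document access (section 11):* nothing is sent.
- *AE listing in 8.5:* comes after the third event is known, so it cannot help reach the count.

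**4. Illustration of size.** Let q be the share of related severe AEs rated definitely, and r the share that does not reach the IME. Both are assumptions. With independent events, the chance that the literal dosing count is still short when the third probably or definitely related severe AE occurs is 1 − [(1 − q)(1 − r)]³.

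| q | r | Chance |
|---|---|---|
| 0 | 0 | 0% |
| 1% | 0 | 1 − 0.99³ = 3% |
| 5% | 0 | 1 − 0.95³ = 14% |
| 10% | 0 | 1 − 0.90³ = 27% |
| 20% | 0 | 1 − 0.80³ = 49% |
| 5% | 5% | 1 − 0.9025³ = 26% |
| 10% | 10% | 1 − 0.81³ = 47% |

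The strict definition of definitely related (other factors excluded, rechallenge if necessary) points to low q. The breadth of the SAE definition points to low r.

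**5. People on study agent at one time.** Accrual is 2 per month (5.3), treatment lasts 6 weeks (6.1.9), one extra week is allowed (6.1.8), and a month is 4.348 weeks.
- Planned: 2 × 6 / 4.348 = 2.8, half of them (1.4) on fluoxetine at 1:1.
- With the extra week: 2 × 7 / 4.348 = 3.2.
- 40 subjects spread over the 2-year study: (40/24) × 6 / 4.348 = 2.3.

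**The case against.** The strongest reply is that nobody would exclude a more certain causal link from a safety halt, so the first limb is wording only. That is right about intent. A reader might infer that the protocol means to ignore definitely related events; the ordered scale in 8.2.2 speaks against it. The wording still needs correcting, because the rule should not rely on its reader to repair it.

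A second reply is that the rest of 8.5 is a safeguard. If the second sentence stands alone, the IME is alerted at the third severe AE of any causality and advises on proceeding. That holds, but only on that reading. A reader might go further and conclude that enrolment is always protected, or that dosing would carry on after enrolment had stopped. Both depend on a sentence that may simply refer back to the one before it.

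Third, the unreported group is narrow. Section 8.2.1 describes severe events as those that interrupt "usual daily activity and may require systemic drug therapy or other treatment. Severe events are usually potentially life-threatening or incapacitating". Section 8.1.2 defines seriousness broadly, including worsening depression and increased seizure frequency, and an event unexpected in severity may reach the IME as an unanticipated problem within 7 days. Section 8.5 itself presumes that qualifying events are reported. All of this stands, and it makes the group small. It does not supply a clock for the remainder. The opposite inference, that such events have no route at all to the IME, is also too strong, given 10.6.3, 8.6 and section 11.

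Finally, the illustrative percentages rest on assumed q and r. That is so, and the conclusion does not need them. An expected number of events before the halt would be less secure still, since it presumes an unlimited supply of events in a 40-subject trial.

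**Conclusion.** Both limbs hold on the text. Section 8.5 literally omits definitely related severe AEs, and its count can miss severe, related, expected, non-serious AEs because no timed report carries them to the IME. Whether the omission also reaches the enrolment stop depends on an ambiguous sentence.

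The practical size is small and cannot be derived from the documents. At the planned accrual a late halt concerns roughly 3 participants on study agent at once (range 2.3 to 3.2), plus any newly enrolled if the second sentence shares the gap. Other protections remain: SAEs reach the IME regardless of relationship, a participant with an SAE is terminated individually (5.4.2), and the study can be suspended for unacceptable risk (5.5). A reader might infer that participants are left without safety oversight, or that the trial's results are compromised; neither follows, and no endpoint or analysis is touched. This is a minor correction to a safety rule, worth making because the rule is the only numerical one and the repair is short.

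**What to change.** - **8.5, first sentence:** make the trigger *three severe AEs (8.2.1) judged probably or definitely related*.
- **8.5, second sentence:** state that IME notification and the enrolment stop occur no later than the third such event. This removes the ambiguity without delaying either action.
- **8.4.1:** add *All severe AEs, serious or not and regardless of relationship, are reported to the IME with their causality rating within 72 hours of site awareness (24 hours if 8.4.2 requires)*. Reporting regardless of relationship lets the IME see events whose rating is later upgraded.
- Keep the threshold of three.

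The cost is a few words in 8.5, one added sentence in 8.4.1, and a few more forms to the IME. The dosing halt may come somewhat earlier for the roughly 3 participants then on study agent. Section 2.3.1 warns about stopping fluoxetine suddenly, so their taper would need attention.

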8.6 SAFETY OVERSIGHT

Safety oversight will be under the direction of an independent medical examiner (IME). The IME will assess safety and efficacy data on each arm of the study. The IME will provide its input to IRB, sponsor and principal investigator

9 CLINICAL MONITORING

NA

10 STATISTICAL CONSIDERATIONS

10.1 STATISTICAL AND ANALYTICAL PLANS

This study is designed as a pilot to obtain estimates to be used in future studies. We will report the descriptive statistics for both treatment groups for each endpoint.

10.2 STATISTICAL HYPOTHESES

No statistical hypothesis

10.3 ANALYSIS DATASETS

Per protocol analysis

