5.4 PARTICIPANT WITHDRAWAL OR TERMINATION

5.4.1 REASONS FOR WITHDRAWAL OR TERMINATION

Participants are free to withdraw from participation in the study at any time upon request. An investigator may terminate participation in the study if:

- Any clinical serious adverse events related or unrelated to the study.
- The participant meets an exclusion criteria (either newly developed or not previously recognized) that precludes further participation.

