5.4.2 HANDLING OF PARTICIPANT WITHDRAWALS OR TERMINATION

If the participant withdraws or terminates participation in the study prior to randomization to one of the intervention arms, no attempt for follow up will be made.

If the participant withdraws or terminates participation in the study after randomization to one of the intervention, we will attempt to contact them via phone calls for safety follow up. No other outcome measures will be collected.

If the participant in the study develops serious adverse events (SAEs), they will be terminated from further participation in the study. They will be referred for appropriate evaluation and treatment (if already not being done). They will be followed up until resolution of the adverse events.

Version 01.2 Protocol:201607761 Version 20.2 Version 01.2

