6.1.7 STARTING DOSE AND DOSE ESCALATION SCHEDULE

10 mg once a day for one week, 20 mg once a day for one week, 40 mg once a day for two weeks, 20 mg once a day for one week and 10 mg once a day for one week. Then STOP.

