7.3.3 FOLLOW-UP

Follow up phone call at end of week 1 and 3

Record for adverse events as reported by the participants.

If suspicious for mania, will perform full Altman self-report maniac scale

Record compliance to assigned treatment as reported by the participants.

Record current medication

Follow up visit 4 weeks (+/-1 week) after randomization

Record for adverse events as reported by the participants.

Record compliance to assigned treatment as reported by the participants and by counting pill from the pill container brought by the participants.

Record PHQ-9 score

Repeat HCVR testing

Record current medication

Video EEG study with comprehensive respiratory monitoring in EMU for paticipants enrolled at neurology clinic

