10.4.2 ANALYSIS OF THE PRIMARY ENDPOINT(S)

Enrollment rate:

This will be assessed every 3 months until the end of the enrollment period. It will be reported as number of participants enrolled per 3 months. It will also be reported as percentage of all the patients screened.

Retention rate:

This will be assessed every 3 months. It will be reported as number of participants completed the study per protocol per 3 months. It will also be reported as percentage of all the patients screened.

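### With an undefined per-protocol set as the only analysis set and outcome collection ending at withdrawal, participants who leave before week 4 drop out of the secondary estimates, and for PHQ-9 that loss can depend on the outcome

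*Combined protocol and SAP*

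**What the plan says.** Section 10.3 reads in full "Per protocol analysis". No section gives criteria for that set, such as a pill-count threshold, a visit window or disqualifying deviations, and no other analysis set is named.

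After withdrawal following randomisation, section 5.4.2 plans attempted phone contact for safety and adds: "No other outcome measures will be collected". The same section says: "If the participant in the study develops serious adverse events (SAEs), they will be terminated from further participation in the study". Section 8.1.2 lists worsening depression in the SAE definition, as an example under persistent or significant incapacity. Section 7.3.5 marks the early termination visit as not applicable.

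Post-baseline outcomes are scheduled once, in 7.3.3: "Follow up visit 4 weeks (+/-1 week) after randomization". That visit carries the PHQ-9 and the repeat HCVR. The list also includes "Video EEG study with comprehensive respiratory monitoring in EMU for paticipants enrolled at neurology clinic". Section 10.4.3 drops observations with missing data.

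Sections 10.1 and 10.4.1 give the purpose: estimates of centre and spread for future studies, with no inferential tests on these endpoints.

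**The concern.** Each rule is common in a pilot. Together they mean that a participant who leaves before week 4 contributes nothing to any estimate of change or of on-treatment peri-ictal breathing. Because PHQ-9 change is a secondary endpoint and worsening depression can be an SAE, the plan can remove a participant because a measured outcome got worse. The means and SDs to be carried into a later trial would then describe only those who stayed. Since the set has no criteria, the choice of who counts could also be made after the data are seen.

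**Working it through.** **Who is lost, from the text.** There are two cases.

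- Leaves before week 4: baseline values only. Nothing further is collected (5.4.2), there is no termination visit (7.3.5), and the missing values are dropped (10.4.3). The mixed models in 10.4.3 do not recover a change score when no post-baseline value exists and the set excludes the person.
- Leaves during the taper in weeks 5-6 (6.1.7: "20 mg once a day for one week and 10 mg once a day for one week"): the week-4 data exist already. Whether they are used depends on the undefined set.

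**Could the loss relate to outcome?** For PHQ-9, yes, by the SAE route. The route is narrow: 5.2 excludes severe depression and PHQ-9 above 20, and 8.1.2 places worsening depression under incapacity, which is more than any rise in score. For HCVR slope the documents give no direct route.

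**Illustration of size.** The plan states no dropout rate, effect size or SD, so it has no figure to reproduce.

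Inputs from the documents: 20 completers per arm (5.3; 4.1 gives 20 completers at each of two locations, randomised 1:1), and about 10 per arm for peri-ictal endpoints, which come only from the 20 clinic-enrolled participants. The 20 per arm for PHQ-9 and HCVR assumes that participants from both locations attend week 4, as 7.3.3 says.

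Assumed: a normal outcome; a fraction d = 5% or 10% lost before week 4 from one arm only; the loss one-sided; correlation r between a latent loss variable and the outcome.

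Formulas: c = z(1-d); L = φ(c)/(1-d); V = 1 - cL - L². Mean shift in that arm = rL. Its variance = 1 - r²(1-V). Pooled variance = the average of that and 1.

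- d = 5%: c = 1.645, L = 0.1031/0.95 = 0.109, V = 0.810.
- d = 10%: c = 1.282, L = 0.1755/0.90 = 0.195, V = 0.712.

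| d | r | mean shift (SD) | pooled variance too low by |
|---|---|---|---|
| 5% | 0.3 | 0.033 | 0.9% |
| 5% | 0.6 | 0.065 | 3.4% |
| 5% | 1 (limit) | 0.109 | 9.5% |
| 10% | 0.3 | 0.058 | 1.3% |
| 10% | 0.6 | 0.117 | 5.2% |
| 10% | 1 (limit) | 0.195 | 14.4% |

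A simulation of the r = 1 limit at these small numbers (200,000 runs) gives 0.09 SD and about 8% for losing 1 of 21, 0.17 SD and about 12% for 2 of 22, and 0.16 SD and about 11% for 1 of 11 (peri-ictal).

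**Sampling error for comparison.** SE of a difference = √(2/n), in SD units. The 95% interval for the true variance, relative to the estimate, is df/χ².

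- n = 20 per arm: SE = √(2/20) = 0.316. With 38 df, 38/56.90 = 0.668 to 38/22.88 = 1.661, that is -33% to +66%.
- n = 10 per arm: SE = √(2/10) = 0.447. With 18 df, 18/31.53 = 0.571 to 18/8.231 = 2.187, that is -43% to +119%.

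Every bias in the table, including the limits, is smaller than the matching sampling error.

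**The case against.** The best defence is that this is a feasibility pilot with no efficacy hypothesis (10.2), and that the scientific question is mechanistic: does fluoxetine raise CO₂ sensitivity? An on-drug set is a defensible choice for that, and off-drug HCVR tests would mix exposures. The bias figures also rest on unfavourable assumptions: similar loss by the same mechanism in both arms would largely cancel in the difference. All of this stands. It argues for keeping an on-drug analysis and for modest weight, but not for leaving that set undefined or for making it the only one.

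Three stronger readings are tempting, and the documents do not support them.

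- A reader might infer that the SD will be too small and the drug effect inflated. That follows only under one-sided selection. Losing participants with little change would raise the SD, and nothing says which arm loses more.
- A reader might infer that the primary endpoints are compromised. Recruitment does not depend on the analysis set. Retention does use the phrase (10.4.2: "It will be reported as number of participants completed the study per protocol per 3 months"), and completion could mean the week-4 visit, the end of the six-week course (6.1.9) or the week-7 call. But 7.3.4 heads that call as the final study visit, which is a natural reading. On the planned denominator of about 100 screened (5.3), each doubtful participant moves the figure by 1/100 = 1 percentage point. This is missing detail.
- A reader might infer that adverse events in leavers are lost. Sections 5.4.2 and 8.3 keep seeking and recording them.

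Section 5.4.1 is permissive on SAEs ("An investigator may terminate participation in the study if") where 5.4.2 is mandatory. That is a drafting mismatch and carries no weight here.

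**Conclusion.** The point holds and is worth fixing, at moderate weight. The text establishes that participants who leave before week 4 are absent from every secondary estimate that needs a post-baseline value, and that for PHQ-9 the plan's own rules can make this absence depend on the outcome. It does not establish the size or direction of any bias. Under the assumed one-arm loss of 5-10%, the distortion is probably below this pilot's sampling error. There is no efficacy test to invalidate. What is at stake is how far the PHQ-9, HCVR and peri-ictal means and SDs can be carried into a later trial, and whether readers can see who is missing from them.

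**What to change.** 1. In 10.3, report secondary endpoints for all randomised participants as assigned, using all available data. Keep a per-protocol (on-drug) analysis alongside, with criteria set before data are seen: for example a pill-count threshold, the week-4 test within its one-week window, and no prohibited drugs.
2. In 5.4.2, separate stopping drug from stopping measurement. Collect the week-4 PHQ-9 by phone during the safety contact already planned. Where the participant consents and it is safe, also obtain the scheduled HCVR and EMU recording.
3. Report numbers randomised, stopped and measured, by arm.

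Minor clarifications: state in 10.4.2 which visit counts as completion, and make 5.4.1 and 5.4.2 agree on SAEs.

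Cost: a short amendment, a questionnaire added to an existing call, and a few off-drug assessments of types already scheduled. The all-randomised estimates will be somewhat diluted as a measure of the on-drug effect, which is why the on-drug analysis stays. Recovery will be incomplete: participants who refuse contact cannot be measured, and rebreathing may be unsuitable after some SAEs, leaving only the PHQ-9.
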